6.1.2.1 Guidelines for Dose Escalation

An escalation to the next dose level is required if a spontaneous bleeding event occurs after the fifth daily dose on a dose level. A dose escalation will not occur if the subject is on the maximum dose level of 120 µg/kg. A spontaneous bleeding episode is defined as one that is precipitated by normal activities of daily living (ADL). Subjects will use their current bypass regimen for any spontaneous or traumatic bleed that occurs while on study drug.

Three dose escalations are allowed during Part 2: 60, 90, and 120 µg/kg (maximum dose).

Safety parameters and PK/PD assessments at each dose level will be monitored to ensure that dose escalation to a higher dose level is appropriate.

The spontaneous bleeding episode must be reported to the clinical team immediately and determination of a dose escalation will be made on review of available clinical information related to the spontaneous bleeding episode and may require subsequent treatment and laboratory data, including available results from the PK/PD/safety assessments.

A decision to proceed with dose escalation will be made by the principal investigator in agreement with personnel who have Sponsor, or designee, medical oversight responsibility.

If there is disagreement amongst any of those individuals, the decision will be reviewed on an urgent basis by an independent Medical Consultant for Safety Oversight.

MAA-201 VERSION 2.0

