9.1 STUDY HYPOTHESIS

The null hypothesis (H0) is that the ABR in all subjects treated with daily SC administration of MarzAA will result in an ABR of 12 as compared to the historical control rate of 12, i.e. H0: ABR (for MarzAA) = 12. The alternative hypothesis (H1): ABR (for MarzAA) < 12.

Primary Endpoint

The primary endpoint will include:

- ABR (spontaneous and total) during Part 2 when on final MarzAA dose level versus recorded historical ABR

Bleeding events will be evaluated as follows:

- Spontaneous vs Traumatic

A spontaneous bleeding episode is defined as one that is precipitated by normal ADL.

MAA-201 VERSION 2.0

Secondary Endpoints

The secondary endpoints will include:

- Occurrence of breakthrough bleeds requiring escalation to higher dose level.
- Safety parameters: Occurrence of clinical thrombotic event not attributable to another cause, and occurrence of antibody formation resulting in a decreased endogenous level of FVII or FVIIa.
- Change in coagulation parameters (PT, aPTT, fibrinogen, MarzAA antigen and activity levels, and TGT) from pre-dose.
- Occurrence of an antibody response to MarzAA and whether it is inhibitory and cross-reactive to wt-rFVIIa or wt-FVII.
- Clinically significant levels of thrombogenicity markers resulting from daily SC administration of MarzAA
- Feasibility and ease of use of daily SC self-administration by patient as measured by compliance with treatment
- Breakthrough bleeding events will be categorized as follows:
 - Number of bleeds that are life threatening
 - Number that require hospitalization and/or blood transfusion
 - Number of muscle bleeds
 - Median time to resolution (and interquartile range) of bleeds

Exploratory Endpoints

- Identification of biomarker(s) such as antigen levels, activity levels, or global thrombosis assay evaluation that can be used to predict or correlate with a subject's lack of spontaneous bleeding.
- Identification of biomarker(s) such as D-dimer, F1+2, or a functional assay of the FVIIa activity that will identify or predict clinical thrombogenicity with the daily SC administration of MarzAA.
- Identification of biomarker(s) such as D-dimer, F1+2, or a functional assay of the FVIIa activity that will identify or predict clinical thrombogenicity of daily SC administration of MarzAA when use of rescue medication is required.
- PRO measures: EQ-5D, VAS; Haem-A-QoL; Hemophilia Activities List (HAL)

MAA-201 VERSION 2.0

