9.4 STATISTICAL ANALYSIS

9.4.1 General Approach

Standard PK parameters such as terminal half-life, AUC_{0-t} and AUC_{0-inf}, clearance, volume of distribution, mean residence time and bioavailability (of the subcutaneous versus the intravenous administration) will be calculated. A semi-parametric model described by Lee et al (1990, 1997) will be used to calculate the terminal half-life. A noncompartmental approach based on the trapezoidal rule will be used to compute the AUCs and the parameters derived from them. Descriptive statistics will be reported for each parameter and will include mean ± standard deviation and median ± interquartile range. The number of subjects requiring dose escalation will be reported.

MAA-201 VERSION 2.0

The analysis of the primary endpoint (annualized bleeding rate) of the final dose used to treat a subject will be based on the evaluation of the ABR of MarzAA compared to a rate seen with on-demand therapy. The latter is assumed to be 12 (or one bleed per month) as our null hypothesis (H0). The comparison of the actual ABR for MarzAA either pooled across all doses used or evaluated at the highest dose for an individual will be compared to this null hypothesized value using the one-sample test for a Poisson rate (using an exact calculation of the p-value based on the program StatXact 11, Cytel, Inc., 2015). Because this will be a one-tailed test (the alternative hypothesis is the ABR for MarzAA will be < 12), a one-tailed 2.5% significance level will be used.

All other statistical tests will be performed at the 0.05 significance level using two-sided tests.

There will be a formal Statistical Analysis Plan (SAP) completed prior to database lock and unblinding of the study data.

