### 4.2 SECONDARY ENDPOINTS

The secondary endpoints will include:

- Occurrence of breakthrough bleeds requiring escalation to higher dose level.
- Safety parameters: Occurrence of clinical thrombotic event not attributable to another cause, and occurrence of antibody formation resulting in a decreased endogenous level of FVII or FVIIa.
- Change in coagulation parameters (prothrombin time (PT), activated partial thromboplastin time (aPTT), fibrinogen, MarzAA antigen and activity levels, and thrombin generation test (TGT)) from pre-dose.
- Occurrence of an antibody response to MarzAA and whether it is inhibitory and cross-reactive to wt-rFVIIa or wt-FVII.
- Clinically significant levels of thrombogenicity markers resulting from daily SC administration of MarzAA
- Feasibility and ease of use of daily SC self-administration by patient as measured by compliance with treatment
- Breakthrough bleeding events will be categorized as follows:
  - Number of bleeds that are life threatening
  - Number that require hospitalization and/or blood transfusion
  - Number of muscle bleeds

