## 8.2 SECONDARY ENDPOINTS AND ANALYSES

### 8.2.1 Analysis of Occurrence of Breakthrough Bleeds and Proportion of Bleeding Days

A breakthrough bleed is any spontaneous or traumatic bleed. Subjects who had breakthrough bleeds out of total bleedings will be summarized separately as spontaneous and traumatic as well as combined and listed using ITT, modified ITT population and per-protocol population.

Breakthrough bleeding events will be categorized and summarized as follows:

- Number and percentage of bleeds that are life threatening for each dose level within each study part
- Number and percentage that require hospitalization and/or blood transfusion for each dose level within each study part
- Number and percentage of muscle bleeds for each dose level within each study part

A listing of breakthrough bleeding events will be provided, including start and end date of bleeding.

Mean pre-treatment between bleeding intervals for all subjects will be compared with post-treatment between bleeding intervals for each dose level in Part 2 using paired t-test. This analysis will only be performed if there are at least 6 data points at pre- or post treatment. The analysis will be performed using ITT, modified ITT and per-protocol population.

The proportion of bleeding days pre-treatment by subject will be compared with the proportion of bleeding days post-treatment for each dose level in Part 2 using paired t-test after transforming the individual proportions by an arcsin transformation ( $2 \cdot \arcsin(\sqrt{p})$ ). This analysis will only be performed if there are at least 6 data points at pre- or post treatment. The proportion of bleeding days pre-treatment will be

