**Version 2.0**

**Syneos Health #1009647**

## **14 CHANGE FROM ANALYSIS PLANNED IN PROTOCOL**

1. Protocol primary efficacy endpoint stated the Poisson analysis will be performed using StatXact 11. However, SAS 9.4 will be used for the exact analyses as specified in this SAP.

Statistical Analysis Plan

Catalyst Biosciences, Inc. Protocol # MAA-201

Version 2.0

Syneos Health #1009647

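### SAP 8.2.1 does not analyse the escalation-bleed secondary endpoint: it counts any bleed, sets subjects against bleeds, and omits time to resolution without declaring the change

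*SAP*

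**What the plan says.** SAP 4.2 lists as its first secondary endpoint "Occurrence of breakthrough bleeds requiring escalation to higher dose level", and Protocol 9.1 has the same item. Protocol 6.1.2.1 gives the trigger: "An escalation to the next dose level is required if a spontaneous bleeding event occurs after the fifth daily dose on a dose level". The same section rules out escalation at the maximum level and makes the decision to escalate a joint one between the investigator and the sponsor's medical oversight. Protocol 6.4 adds a condition: after two or more missed doses, a spontaneous bleed counts only from 4 days after dosing resumes.

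SAP 8.2.1, the matching analysis section, states: "A breakthrough bleed is any spontaneous or traumatic bleed. Subjects who had breakthrough bleeds out of total bleedings will be summarized separately". The rows it then names are spontaneous, traumatic and combined.

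Protocol 9.4.1 commits to a further output: "The number of subjects requiring dose escalation will be reported". Protocol 3.2 and 9.1 also list "Median time to resolution (and interquartile range) of bleeds". SAP 14, on changes from the protocol, has one item, the move from StatXact to SAS, ending: "However, SAS 9.4 will be used for the exact analyses as specified in this SAP".

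**The concern.** Part 2 of the trial looks for the dose at which each subject stops bleeding spontaneously. The share of subjects who fail a level by the protocol's own rule is the most direct dose-finding result the trial can give. A programmer who follows SAP 8.2.1 as written would tabulate a different event, on a scale that cannot be read as a rate of failure. The protocol's promised count of escalated subjects would depend on someone deriving it from other tables. The loss of time to resolution removes a second listed result. Because neither change is declared, a reader of the study report could not tell whether they were intended.

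**Working it through.** The plan states no figure for this endpoint, so there is nothing to reproduce. The check compares the sections and then works through the ratio.

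**1. The event.** SAP 8.2.1 against the criterion in Protocol 6.1.2.1 and 6.4:

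| Bleed | Counted in SAP 8.2.1 | Can require escalation |
|---|---|---|
| Spontaneous, after the fifth dose, below the maximum level | yes | yes |
| Spontaneous, before the fifth dose on a level | yes | no |
| Spontaneous, less than 4 days after resuming from two or more missed doses | yes | no |
| Spontaneous, at 120 µg/kg | yes | no |
| Traumatic | yes | no |

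The split into spontaneous and traumatic removes only the last row. The fifth-dose, missed-dose and maximum-level conditions are applied nowhere.

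**2. The ratio, read literally.** Let S be subjects with at least one bleed, B total bleeds and N = 12 planned subjects. The SAP ratio is S/B; the ordinary subject proportion is S/N.

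| S | B | S/B | S/N |
|---|---|---|---|
| 4 | 8 | 50% | 33% |
| 4 | 20 | 20% | 33% |
| 8 | 12 | 67% | 67% |
| 4 | 4 | 100% | 33% |
| 8 | 8 | 100% | 67% |

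From row 1 to row 2 bleeding worsens and S/B falls. From row 1 to row 3 it worsens and S/B rises. From row 4 to row 5 it worsens and S/B does not move.

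**3. Expected size under a simple model.** Assume Poisson bleeding, the same rate in every subject, and 50 days at one level. Mean bleeds per subject are m = ABR × (50/30.5)/12, using the SAP's 30.5-day month. Expected bleeds are Nm and expected bleeding subjects are N(1 − e^(−m)), so S/B is about (1 − e^(−m))/m and the subject share is 1 − e^(−m).

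| ABR | m | S/B | Subjects with any bleed |
|---|---|---|---|
| 6 | 0.82 | 68% | 56% |
| 12 | 1.64 | 49% | 81% |
| 24 | 3.28 | 29% | 96% |

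If the rate rises uniformly, the two measures move in opposite directions. The model ignores that a qualifying bleed below the maximum level ends time at that level, so it shows behaviour and is not a forecast.

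The any-bleed event also differs in size from the escalation event. Let q be the spontaneous share of bleeds. The documents do not give it; 0.5 to 1.0 is assumed. The qualifying window is the 45 days after the fifth dose, so the expected share is 1 − exp(−q × ABR × (45/30.5)/12). At ABR 6 this is 31% (q = 0.5) to 52% (q = 1.0), against 56% with any bleed.

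**4. The ratio, read as bleeds over bleeds.** Every bleed is a breakthrough bleed by the SAP's definition, so the combined row is B/B = 100%. The spontaneous and traumatic rows are then an ordinary split of all bleeds.

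**5. Is escalation reported elsewhere?** SAP 8 summarises efficacy by final dose level, SAP 12.1 gives exposure by level, and SAP 15.2.4 puts N in column headings. SAP 11.3 mentions the frequency of escalated subjects, but within antibody summaries. No section specifies a count or proportion of subjects who required escalation.

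**6. Time to resolution.** It is absent from SAP 4.2 and 8.2.1. Protocol 8.1 collects onset and resolution date and time in the eDiary, and SAP 8.2.1 lists start and end dates, so the data are there. SAP 9.6 and 10.7, the other notes on departures, mention only the added PK and PD populations.

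**The case against.** The strongest reply is that little is lost. SAP 4.2 keeps the escalation wording, the protocol's commitment in 9.4.1 is not withdrawn, and the protocol itself uses the term breakthrough loosely: its list of bleed categories in 9.1 carries no escalation condition, though 3.2 attaches one. The share escalating from the first level can largely be read from the column sizes. The sentence on subjects and bleeds never mentions a percentage, and the table conventions in SAP 15.2.5.2 make subjects the default denominator. Bleed dates are listed and bleed intervals graphed. All of these outputs are descriptive, in a 12-subject Phase 2 trial.

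Part of this stands. A reader might infer that the endpoint is not measured at all. The documents do not support that: the data are collected and escalations can be partly inferred. They can be only partly inferred because escalation is a reviewed decision, de-escalation is possible (Protocol 6.1.2.2) and subjects may withdraw (Protocol 7.2), so final level need not match qualifying bleeds. A reader might also infer that the ratio must fall as bleeding worsens, or that any bleed-level ratio is 100%. The first fails on rows 3 to 5 of the second table above; the second holds only for the combined row.

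The rest does not rescue the text. The default denominator applies only where nothing else is noted, and this sentence names total bleeds. Keeping the endpoint in SAP 4.2 does not help when the analysis section drops its defining condition.

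**Conclusion.** The point holds as a mismatch between a listed endpoint and its specified analysis. SAP 8.2.1 analyses a wider event than the one listed, with a denominator that mixes units under one reading and is uninformative in its combined row under the other. The protocol's escalation count has no specified output, median time to resolution is dropped, and SAP 14 declares neither change.

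The comparison of sections needs no assumption. The 50% and 20% figures are arithmetic on an example. The expected values rest on a homogeneous Poisson rate, a fixed 50 days at one level and an assumed spontaneous share, and only show direction and rough size. No benchmark for the no-effect escalation share is offered, because the documents give no spontaneous rate to base it on. The primary ABR analysis is untouched. The SAP should be corrected, but the matter is one of secondary, descriptive results.

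**What to change.** In SAP 8.2.1:

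1. For each dose level below the maximum, report n/N (%) with an exact 95% CI for subjects with a bleed meeting the protocol's existing criterion (Protocol 6.1.2.1 and 6.4). N is subjects at risk at that level, with at-risk status defined in the SAP. Alongside it, report the number actually escalated, since the decision is reviewed and may differ from the rule. A summary of the same event at the maximum level is optional.
2. Report any, spontaneous and traumatic bleed occurrence as subjects over subjects treated at that level.
3. Restore median (IQR) time to resolution, here and in SAP 4.2, from the eDiary onset and resolution times.
4. Record any intended departure from the protocol in SAP 14.

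The cost is SAP wording and about two table shells. No new data are needed.

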4.2 END OF STUDY DEFINITION

The minimum duration of treatment for each subject is approximately 2 months (if no dose escalation is required) and the maximum duration is approximately 7 months (if three dose escalations are required).

Up to 4 weeks for screening period; 24 hours for the part 1a (single IV dosing and PK/PD/Safety testing); 48 hours for the Part 1b (single SC dosing and PK/PD/safety testing); and up to 197 days of daily SC dosing and a PK/PD/safety follow-up assessment 30 days after last dose. Subjects must have no spontaneous bleeding for 50 days if on the first three dose levels or complete 50 days of treatment on the fourth dose level. The end of study visit will be 30 days after the last dose of study drug treatment in Part 2.

A participant is considered to have completed the study if he has completed all phases of the study, including treatment at the same dose level for 50 days, and returned for procedures listed under end of study visit as shown in the SOA.

MAA-201 VERSION 2.0

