#### Part 2: Daily SC administration

At Day 1 of daily SC dosing, subjects will begin their self-administered dosing regimen. MarzAA will be self-administered by subjects daily (at approximately the same time every day), starting with a SC dose of 30 µg/kg MarzAA. At each dose, subjects will record the day and time of the SC injections in their diary. If a spontaneous bleeding episode (defined as one that is precipitated by normal activities of daily living [ADL]) occurs before the fifth daily dose, subjects will continue at the current dosing level. If a spontaneous bleeding episode occurs after the fifth daily dose, the MarzAA dose will be escalated to the next dose level. Three dose escalations are allowed during part 2: 60, 90, and 120 µg/kg (maximum dose). At each dose level escalation, safety and PK/PD will be monitored to ensure that dose escalation to a higher dose level is appropriate. If a subject requires a third dose escalation to the fourth dose level, then they will continue treatment with that dose for 50 days and complete the study, regardless if a spontaneous bleeding episode occurs during the highest treatment dose level.

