- After Day 42, sampling will be done every two (2) weeks until the End of Study visit.
- PRO scales (Appendix B): EQ-5D, VAS; Ham-A-Gol; HAL.
- Subjects must have been at the same dose level for 50 days to complete the study.
- At an Unscheduled Visit, perform only the assessments as appropriate to the reason for the visit.
- End of Study Visit will occur 30 days after the last dose.

This document is proprietary and confidential to Syneos Health LLC.  
Page 21 of 76

03.007A.03

Statistical Analysis Plan

Catalyst Biosciences, Inc. Protocol # MAA-201

Version 2.0

Syneos Health #1009647

Table 4. Part 2: If spontaneous bleeding occurs after the fifth daily dose (only if necessary)

Study Period	Treatment									
	Day 0* (+1d)	Day 7 (±2d)	Day 14 (±2d)	Day 21 (±2d)	Day 28 (±3d)	Day 42 (±3d)	Day 50 (+3d)	Un- scheduled 	End of Study 	
Medical and Hemophilia History 	X	X	X	X	X	X	X	X	X	X
Concomitant Medications	X	X	X	X	X	X	X	X	X	X
Vital Signs	X	X	X	X	X	X	X	X	X	X
Weight	X	X	X	X	X	X	X	X	X	X
Physical Examination	X	X	X	X	X	X	X	X	X	X
Clinical Signs of Thrombosis 	X	X	X	X	X	X	X	X	X	X
Hematology and Chemistry 	X	X	X	X	X	X	X	X	X	X
Coagulation Assays 	X 	X	X	X	X	X	X	X	X	X
Thrombogenicity markers 	X	X	X	X	X	X	X	X	X	X
Pharmacokinetic (PK) sampling 	X 	X	X	X	X	X	X	X	X	X
Immunogenicity assays 	X 	X	X	X	X	X 	X	X 	X	X
Troponin level 	X	X	X	X	X	X	X	X	X	X
Diary entry of PRO scales 	X	X	X	X	X	X	X	X	X	X
Diary entry of IP, bleeding episodes and treatment, AEs, injection site assessment	X	X	X	X	X	X	X	X	X	X
Adverse Events	X	X	X	X	X	X	X	X	X	X
SC Daily MarzAA administration 										
IP compliance & proficiency confirmation	X	X	X	X	X	X	X	X	X	X
IP dispensing, inventory and accountability	X	X	X	X	X	X	X	X	X	X

\* NOTE: When a spontaneous bleeding episode and dose escalation occurs, the "day count" is reset to zero. The day the spontaneous bleeding episode occurs and subsequent time until treatment resolution is considered Day 0. Dose escalation starts the next day (Day 1).

\*\* Assessments performed on Day 7, 14, 21, 28, 42, and 50 will be done pre-dose, unless otherwise specified.

- Interim targeted evaluation, per Investigator's discretion, as indicated on presentation of subject at study visit and review of diary entries (including PRO scales).

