**Statistical Analysis Plan**

Catalyst Biosciences, Inc. Protocol # MAA-201

Version 2.0

Syneos Health #1009647

calculated as (cumulative number of bleeding days recorded in bleed history / 180). The proportion of bleeding days post-treatment will be calculated as (cumulative number of bleeding days from the first SC dose to last dose in eDiary in Part 2 / cumulative number of actual treatment days for each dose level in Part 2). The analysis will be performed using ITT, modified ITT and per-protocol population.

Graphic presentation will also be provided for the interval of each bleeding event and each subject.

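### With 180 days before treatment and a shorter window on treatment, the arcsine-transformed bleeding-days test has a non-zero null difference; the bias is modest, and selection by the escalation rule outweighs it

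*SAP*

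**What the plan says.** SAP 8.2.1 plans a before/after comparison of bleeding days for each Part 2 dose level, "using paired t-test after transforming the individual proportions by an arcsin transformation". The transform is 2·arcsin(√p).

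- Pre-treatment proportion: "cumulative number of bleeding days recorded in bleed history / 180".
- On-treatment numerator: "cumulative number of bleeding days from the first SC dose to last dose in eDiary in Part 2".
- On-treatment denominator: "cumulative number of actual treatment days for each dose level in Part 2".

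SAP section 8 makes every test other than the primary one two-sided at 0.05, which leaves 2.5% for a false fall. It also reports efficacy by final dose level. The analysis runs only with at least 6 data points. No weight, offset or correction for unequal windows is given.

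Three rules fix how long a level lasts. SAP 3.8: "Subjects must have been at the same dose level for 50 days to complete the study". SAP 3.6 escalates the dose "If a spontaneous bleeding episode occurs after the fifth daily dose". Protocol 4.2: "Subjects must have no spontaneous bleeding for 50 days if on the first three dose levels". Only the fourth level (120 µg/kg) runs for 50 days whatever the bleeding.

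**The concern.** A paired t-test of transformed proportions is centred on zero only if the transform has the same expectation in both periods when bleeding is unchanged. The function 2·arcsin(√p) is concave for p below 0.5, so its mean falls as the proportion becomes noisier. At 12 bleeds/year the 180-day history holds 12 × 180/365.25 = 5.9 expected bleeds, and a 50-day level holds 12 × 50/365.25 = 1.6. The on-treatment value is therefore pulled down further, with no drug effect.

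Bleeding days also cluster within bleeds, so the binomial variance that the transform is meant to stabilise does not apply. The transform adds bias with no offsetting benefit. At stake is the error rate of a planned inferential comparison of bleeding before and on the product.

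**Working it through.** The documents give no operating figure for this test. The stated power belongs to the primary Poisson test and does not bear on it.

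**Inputs from the documents:** 180-day history; 50 days at a completed level; 12 subjects, minimum 6 data points; two-sided 0.05; entry ABR of at least 12 (12, 18 and 24 used as a range). **Assumed:** bleed duration (mostly 3 days), Poisson onsets, between-subject CV of 0 to 0.5.

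**1. Direction.** For g(p) = 2·arcsin(√p) and n independent days, the second-order bias is −(1−2p) / (4n·√(p(1−p))). It is negative for p < 0.5 and grows as n falls.

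**2. Exact binomial expectation.** With 1-day bleeds at 12/year, p = 12/365.25 = 0.033. E[g] is 0.356 at n = 180 and 0.318 at n = 50, a difference of −0.038 with nothing changed. At p = 0.131 the difference is −0.009, so the bias shrinks as bleeding becomes more frequent.

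**3. Size with clustered bleeds.** At 12/year, CV 0.5, 3-day bleeds and 180 vs 50 days, the raw means agree (0.092 vs 0.091) but the transformed means are 0.584 vs 0.515. Back-transforming with sin²(x/2) gives 0.083 vs 0.065, an apparent fall of about 22%.

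**4. Significant false fall, fixed 180/50-day windows, 3-day bleeds** (20,000 null trials per cell; arcsine / untransformed; nominal 2.5%):

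| Bleeds/year | n=12, CV 0 | n=12, CV 0.4 | n=6, CV 0 | n=6, CV 0.4 |
|---|---|---|---|---|
| 12 | 6.0% / 3.5% | 7.0% / 3.4% | 3.0% / 3.6% | 4.0% / 3.9% |
| 18 | 3.9% / 3.2% | 4.9% / 3.3% | 2.5% / 3.2% | 2.9% / 3.2% |
| 24 | 3.4% / 3.0% | 3.9% / 3.1% | 2.5% / 3.0% | 2.8% / 3.2% |

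At 12/year with 12 subjects and CV 0.5, the arcsine figure is 7.2-8.8%, against 3.5-4.6% untransformed. With equal 180-day windows the arcsine figure returns to 2.3-2.7%. The cause is therefore the transform combined with unequal windows.

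**5. Escalation rule applied, no drug effect** (12 subjects, equal rates, all bleeds spontaneous, level-specific numerator, 1- and 3-day bleeds). At 30 µg/kg and 12/year, 24% of subjects complete 50 days and the median stay is 27 days. The arcsine difference there is positive (+0.05 to +0.12), with a false fall in under 1% of trials and a false rise in about 10%. At the final level, the false fall is:

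| Bleeds/year | Arcsine | Untransformed | Added by the transform |
|---|---|---|---|
| 12 | 75-80% | 50-57% | 23-25 points |
| 18 | 37-45% | 22-32% | 13-14 points |
| 24 | 16-23% | 12-19% | 4-5 points |

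**6. Literal numerator.** As worded, the numerator covers all of Part 2 while the denominator is one level. Take a subject who leaves 30 µg/kg after 10 treatment days and has four 3-day bleeds in Part 2. His value for that level is 12/10 = 1.2, where the arcsine is undefined. In the step 5 simulation at 12/year, this reading gives a proportion above 1 for 0.4% of subjects (1-day bleeds) to 15% (3-day bleeds).

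**The case against.** The strongest reply is that twelve subjects with a fixed 50-day window hardly occurs. The only level with a fixed window is 120 µg/kg, reached after three escalations. At 12/year with no drug effect, the chance of a spontaneous bleed between the fifth dose and day 50 is 1 − exp(−12 × 45/365.25) = 0.77. The chance of three in a row is 0.46, so about 12 × 0.46 = 5.5 subjects get there, and all twelve do with probability 0.46¹² ≈ 0.0001. Near 6 subjects the transform hardly matters: across the settings tried it is sometimes better than raw proportions and at most about 1.4 points worse. This stands.

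It also stands that 12/year is the entry floor, so the 18-24/year rows are at least as relevant. Proportion of bleeding days is not among the secondary endpoints listed in SAP 4.2, and the primary test is separate.

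A reader might infer that this test shows a fall whenever nothing has changed, or always favours the drug. The documents do not support that. A short level normally ends on a bleed, which can reverse the sign. The sign then depends on how the terminating bleed is counted: counted in full the difference is positive, and counted for its first day only it turns negative. SAP 8.2.1 does not say which. The literal numerator also works against the drug for anyone who escalates. Nor does the fixed-window bias explain most of the final-level fall. That fall comes from keeping the first three levels only when 50 days pass without a spontaneous bleed, and about half of null trials at 12/year remain falsely significant without the transform.

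The reply does not rescue the transform, which still adds 4 to 25 points to the final-level false fall in step 5.

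**Conclusion.** The concern holds in limited form. Unequal windows give the arcsine comparison a null difference that is not zero and lies towards a fall. With fixed 180/50-day windows and 12 subjects, a significant false fall occurs in about 6-9% of null trials at 12/year and about 3-6% at 18-24/year. The nominal figure is 2.5%, and untransformed proportions give about 3-4.6%. With 6 subjects the transform is essentially no worse than raw proportions.

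These figures rest on assumed bleed durations and between-subject spread, and they leave out the escalation rule. With that rule applied, the direction can reverse at a level ended by a bleed. At the final level the larger part of the false fall is selection, which removing the transform reduces but does not cure. The claim that the test generally favours the drug goes beyond the evidence. The change is worth making because it is cheap and the transform brings no benefit here.

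**What to change.** In SAP 8.2.1:

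1. Delete the arcsine transformation.
2. Restrict the on-treatment numerator to bleeding days at the same dose level as the denominator, and state how the days of a bleed that ends a level are counted.
3. Compare bleeding days with a count model: log(days observed) as offset, subject as cluster or stratum, and a subject-level robust variance. At minimum, use the paired difference of untransformed proportions.
4. State that the per-level and final-level comparisons remain affected by bleed-triggered escalation and are descriptive.
5. If a conditional binomial test on bleed counts is used as well, do not claim that it holds its level. It treats days at a level as fixed, and here bleeding determines them. It also tests bleeds rather than bleeding days.

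Cost: SAP wording and a few lines of code, with no new data. The final-level result will probably look somewhat less favourable to the product.
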